Hypothesis 3: Better Treatment Attendance. Integrated clients will attend more behavioral therapy sessions and medication management sessions than Behavioral Only clients.

Hypothesis 4: Greater Medication Acceptance and Treatment Satisfaction. Integrated clients will more often consent to medication, show greater medication compliance, and report greater overall satisfaction than Behavioral Only.

Aim 3: Examine Patient-Centered Outcomes

Research Question 1: Heterogeneity of Treatment Effects. Will clients with co-occurring substance use problems have worse treatment outcomes than those without? Will there be outcome differences based on age, ethnicity, sex?

Research Question 2: Analysis of Individual Differences. Across treatment conditions, will clients who choose to start a medication regimen have better treatment outcomes than those who do not?

Study Design

This study emphasizes ecological validity: Both protocols will be implemented in existing outpatient behavioral services by agency clinicians. To promote internal validity, randomization will occur within site at both the client and therapist level (i.e., study therapists at

each site will be randomly assigned to condition). The primary benefit of “doubly randomized” designs is that they minimize potential bias related to site effects—because randomization occurs within each site—and therapist sampling bias—because therapists are randomly assigned to condition. The use of a Behavioral Only condition will control treatment expectancy effects. Therapists will be trained and supervised to implement CASH-AA and MIP as part of their otherwise routine duties; that is, the protocols will be additional components of their usual practice for study cases. To maximize protocol exposure, and to promote consistency in the timing of protocol implementation across conditions and cases, therapists will be asked to implement CASH-AA and MIP at the start of treatment (unless contraindicated).

Note: (1) ADHD medication will be available to all Behavioral Only cases via routine site practices for ADHD treatment; and (2) MIP supports family decision-making about medication but does not require families to start a medication regimen.

Sample Description

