intensive family engagement and family-agency coordination efforts to help families overcome barriers to enrolling in services, procedures especially valuable for enrolling hard-to-engage families. Linking procedures will cease upon completion of the first intake interview (after which randomization will occur). After linking is completed, research staff will maintain contact with families solely to complete follow-up interviews, which will occur with every randomized family regardless of treatment attendance.

Randomization to study condition and therapist assignment. Cases will be randomly assigned to study condition after completing an intake interview at the assigned site. Urn randomization will promote balance between conditions on 3 variables: sex, ethnicity (Hispanic, African-American, Other), and ASU problems (Yes, No). Once randomized, cases will be assigned to a study therapist in alternate turns. Note that in some sites, it will be necessary to follow “nearly random” assignment to condition, if the given site assigns cases to clinicians based on a shared rotation of case assignment. That is: Any given case is assigned to the next available clinician in the duty rotation, or, the clinician who is on duty during the given intake appointment. Treatment site therapists who agree to participate as study therapists will be consented in their private offices by research staff. We anticipate some degree of therapist dropout due to staff turnover during two years of enrolling study cases. When a study therapist drops out in either condition, the given site will be asked to nominate two potential replacements, and the new therapist will be randomly selected from that pair. All partnering treatment sites will be in close proximity to assigned study participants and easily accessible via public transportation. Each site will routinely prescribe weekly treatment sessions and offer in-house psychiatric support for all cases. All therapists at each site who treat adolescent clients and who volunteer to participate will be accepted into the study randomization pool.

Study Conditions

Behavioral Only Condition: Changing Academic Support in the Home for Adolescents with ADHD (CASH-AA)

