Study therapists will be asked to provide four kinds of study data: (1) Upon consenting to participate in the study, therapists will complete one questionnaire documenting their demographic characteristics and clinical training background, and a second questionnaire documenting their clinical strengths and preferred clinical practices. (2) When treating study cases, therapists will complete and submit the CASH-AA fidelity checklist and, for those in the Integrated condition, the MIP fidelity checklist after every session; and each condition will complete a brief checklist of evidence-based practices for adolescent behavior problems; all checklists (total completion time: 5 minutes) will be collected by research staff on a regular basis. (3) When treating study cases, therapists will audiorecord every session with consenting clients and submit the recordings to research staff on a regular basis. (4) Upon closing a study case, therapists will complete a termination summary of clinical activity that documents information about sessions held, participants in sessions, and treatment procedures that were the main foci of session activity.

Data Analysis

Preliminary Analyses and Refuser Analyses

All analyses will be preceded by examining distributional properties of variables, outliers, and need for using transformed variables or non-parametric tests. We will examine whether randomization successfully created equivalent study groups by conducting *t*-tests or chi-square tests on demographics and other variables; those that differ between groups will be entered as covariates in subsequent analyses. Logistic regression will examine potential biases due to failure to contact clients at follow-up on baseline characteristics, study condition, and their interactions. These analyses will determine whether the followed sample differs from the randomized sample and whether there is differential attrition by condition. Also, analyses on refuser characteristics will be conducted to inform the generalizability of the sample, as follows. Families completing the phone eligibility screening instrument will provide information on personal and family demographics. Families of eligible adolescents who refuse to participate in the baseline interview, or who participate in the baseline interview but do not complete an intake appointment at the assigned treatment site, will be asked to complete a brief study refuser

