LGC will proceed using Mplus version 7, as follows. First, we will test a series of growth curve models for each outcome, representing three forms of growth (no change, linear change, quadratic change), to determine the overall shape of the individual change trajectories; overall model fit will be evaluated by examining the chi-square, RMSEA, CFI, and TLI indices. Second, we will test unconditional models for all outcomes to obtain the average effect for change over time in outcome, without including treatment condition or other covariates. Third, we will add the two predictors, Condition (Behavioral Only vs. Integrated) and baseline Substance Use (SU+ vs. SU-) to the models in order to test the impact of each predictor on initial status and change over time. We will also test Condition X SU interactions, and if any are significant for a given outcome, we will re-run that model separately for the SU+ and SU- participants to test simple effects. Treatment effects (Aim 1) for any given outcome will be shown by a statistically significant effect parameter, as tested by the pseudo z test—calculated by dividing the coefficient by its standard error—associated with Condition. Heterogeneity of Treatment Effects (HTE; Aim 3) for any given outcome will be identified by a significant effect for the Condition X SU interaction term; post-hoc analyses will be used to explore these interactions to determine whether Integrated effects appeared to be stronger or weaker in SU+ versus SU- cases. Initially, all models will be adjusted for nuisance covariates: sex, age, and ethnicity; family income; caregiver education level; and treatment site. We will then further explore HTE (Research Question 1) by testing for outcome differences based on age, ethnicity, and sex subgroups. Per above we will use the sandwich estimator to control for therapist nesting. Effect size estimates for significant findings in Aims 1 and 3 analyses will be calculated based on Feingold's procedures for calculating effect sizes for LGC analyses. Also, for any outcome that deviates substantially from normality—typical for delinquency and SU data—we will use two-part growth curve models, which allow for the simultaneous estimation of separate but correlated continuous and categorical LGC models. Two-part models are used when a large number of participants report the absence of the given variable (i.e., no delinquent activities or SU), resulting in highly skewed data. In two-part models, the original distribution of the outcome is separated into categorical and continuous parts, each modeled by separate but correlated growth functions. In the categorical part, a binary indicator variable is created to indicate any vs. none of the outcome in question. The continuous part models the frequency of occurrence of the outcome given any positive occurrence.

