
Finally, for Research Question 2 pertaining to Individual Differences, we will use methods in which days of ADHD medication use since study entry is positioned as a predictor of client outcomes. Because medication use will be dependent on client choice and not randomly assigned, the first step is to create 2 new groups: High Use vs. Low/No Use (or 3 groups, depending on data distributions). This will be done via propensity score matching analyses for ordinal treatment variables. Propensity scores will be calculated using an ordinal logit model to represent each client's probability to be medicated over time as a function of multiple baseline variables presumed to influence medication choice (condition, demographics, ADHD symptom severity, comorbid symptoms). Clients will be matched on these variables to minimize differences in propensity scores and maximize differences in medication use days at 12-month FU. This will statistically control for observed variables that might influence the likelihood of natural selection into medication use over time. Once propensity score-based groups are created, we will conduct matched-pair analyses for each outcome, using dependent *t*-tests for continuous and McNemar's chi-square test for dichotomous variables⁷⁸.

Plan of Analysis for Main Outcomes: Aim 2

Multilevel modeling will examine Condition effects on time-invariant client outcomes: treatment attendance, medication acceptance, and client satisfaction (averaged across caregiver and adolescent); separate models will be run for each variable. Outcomes will be analyzed using multilevel regression analysis with random intercepts and slopes in Mplus version 7. Condition will be entered as a level-1 predictor and regressed directly on the outcome variable; the influence of the predictor is examined by testing the significance of the effect parameter. As discussed above, to control for therapist nesting effects we will use the sandwich estimator; all models will be adjusted for the nuisance covariates listed above; and missing data will be handled with robust maximum likelihood estimation (see below).

Analytic Plans for Missing Data

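### Aim 2 models leave out baseline substance use, the one urn-balancing factor missing from their covariate list; the cost is at most a modest loss of precision, not a validity error

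*Combined protocol and SAP*

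**What the plan says.** Four parts of the combined protocol and SAP bear on this.

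- **Allocation.** Under Randomization to study condition and therapist assignment: "Urn randomization will promote balance between conditions on 3 variables: sex, ethnicity (Hispanic, African-American, Other), and ASU problems (Yes, No"). I read ASU as adolescent substance use. Study Design adds that "randomization will occur within site at both the client and therapist level".
- **Aims 1 and 3.** The growth models bring substance use in by name: "we will add the two predictors, Condition (Behavioral Only vs. Integrated) and baseline Substance Use (SU+ vs. SU-) to the models". A separate sentence then says that "all models will be adjusted for nuisance covariates: sex, age, and ethnicity; family income; caregiver education level; and treatment site". Substance use is not in that second list, and there it does not need to be.
- **Aim 2.** The outcomes are "treatment attendance, medication acceptance, and client satisfaction (averaged across caregiver and adolescent"). For the predictor, "Condition will be entered as a level-1 predictor and regressed directly on the outcome variable". For adjustment, "all models will be adjusted for the nuisance covariates listed above". Therapist nesting is left to the sandwich estimator. Substance use is not mentioned.
- **Preliminary analyses.** Arms are compared at baseline, and "those that differ between groups will be entered as covariates in subsequent analyses".

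**The concern.** As written, Aim 2 adjusts for two of the three urn factors and for site, and gives no reason for dropping the third. It looks like a drafting gap: the sentence for Aim 2 borrows the nuisance list, and substance use was never on that list because Aims 1 and 3 handle it elsewhere.

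When allocation is balanced on a factor that predicts the outcome, a model without that factor counts its variation as noise, although balancing has removed some of it from the comparison of arms. The standard error is then too large and the test conservative. Hypothesis 3 (attendance) and Hypothesis 4 (medication acceptance and satisfaction) would lose some precision that the design has already paid for.

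The plan itself gives some reason to expect relevance. For Research Question 2, the propensity model treats comorbid symptoms as an influence on the choice of medication, and Hypothesis 1 counts drug use among comorbid problems. Research Question 1 asks whether clients who use substances do worse.

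**Working it through.** **No figure to reproduce.** The documents give 140 clients in two equal conditions, but no alpha, power, effect size or SD, and no association between substance use and any Aim 2 outcome. What follows shows scale under stated assumptions.

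**Inputs from the documents.** N = 140, 70 per arm. Prevalence of substance use p = 0.2 to 0.5: the eligibility criteria give 20-50%, and the Project Abstract gives half.

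**Assumed.** d, the difference between users and non-users in within-group SD units: 0, 0.2, 0.5, 0.8. Two-sided alpha 0.05.

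**Attendance and satisfaction (linear model).**

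- Share of variance explained: R² = d²p(1−p) / (1 + d²p(1−p)).
- Interval width with substance use relative to without: √[(1−R²) × 138/137]. The second factor is the residual degree of freedom spent.
- Example, d = 0.5 and p = 0.5: d²p(1−p) = 0.0625; R² = 0.0625/1.0625 = 0.0588; ratio = √(0.9412 × 1.0073) = 0.974; so the interval without substance use is 1/0.974, or 2.7% wider.

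| d | R², p = 0.2 | Wider by | R², p = 0.5 | Wider by |
|---|---|---|---|---|
| 0 | 0 | −0.4% | 0 | −0.4% |
| 0.2 | 0.006 | about 0% | 0.010 | 0.1% |
| 0.5 | 0.038 | 1.6% | 0.059 | 2.7% |
| 0.8 | 0.093 | 4.6% | 0.138 | 7.3% |

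A simulation (2,000 runs per setting, N = 140, urn on sex, ethnicity and substance use, both models adjusted for sex and ethnicity, p = 0.3 and 0.5) agrees: 0.3% wider at d = 0.2, 2.4% to 2.9% at 0.5, and 6.4% to 7.7% at 0.8. At d = 0 the model without substance use was 0.2% narrower.

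**Direction of the error.** Under exact balance, type I error without substance use is 2[1 − Φ(1.96/√(1−R²))]. At p = 0.5 this is 0.049, 0.043 and 0.035 for d = 0.2, 0.5 and 0.8. These are limiting values. In the simulation at p = 0.5 the SD of the imbalance was 0.060, against √(0.25 × 2/70) = 0.085 under simple randomization. The urn thus removes about half of the imbalance variance ((0.060/0.085)² ≈ 0.5), and the test is less conservative than the limit.

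**Power.** If power is 80% without substance use (a Condition effect of about 0.47 SD at 70 per arm), it is about 80.4%, 82.3% and 85.5% with it, for d = 0.2, 0.5 and 0.8 at p = 0.5. This takes the unadjusted estimate to vary as its own standard error says. Under exact balance, power without substance use is already Φ(0.84/√(1−R²)), or 80.1%, 80.7% and 81.8%, so the gain is smaller.

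**Therapist clustering.** Therapists are randomized to condition, so the Condition variance includes a between-therapist part that a client-level covariate mostly leaves alone. Assume an intraclass correlation of 0.05 and 10 clients per therapist. The within-therapist share is 0.95/(0.95 + 10 × 0.05) = 0.655. Leaving the degree-of-freedom term aside, the standard error is larger by 1/√(1 − 0.655R²) − 1. At p = 0.5 this gives 2.0% instead of 3.1% for d = 0.5, and 4.8% instead of 7.7% for d = 0.8.

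**Medication acceptance (yes/no).** Assume acceptance of 30% versus 50%, p = 0.5, and an odds ratio for substance use of 1.5 to 3.

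- Logistic, without substance use: log odds ratio = ln(0.7/0.3) = 0.847; SE = √[1/(70 × 0.21) + 1/(70 × 0.25)] = 0.354; z = 2.39.
- Logistic, with substance use: log odds ratio 0.856 to 0.908; SE 0.356 to 0.368; z = 2.40 to 2.47. The interval does not narrow, but z rises slightly.
- Risk difference: SE 0.0811 without, 0.0807 to 0.0783 with, so the interval without is 0.5% to 3.5% wider.

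**The case against.** The best defence is that nothing here threatens validity. Leaving out a balanced covariate errs on the conservative side, and if the arms turn out to differ on substance use, the preliminary-analysis rule brings it in. That defence largely stands. The rule is only a partial safeguard, though: it acts on a detected imbalance, which the urn makes unlikely, and does nothing for precision when the arms are balanced. Balance is also not assured everywhere, because some sites may allocate by clinicians' duty rotation. Prespecifying the factor is cleaner than relying on a baseline test.

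A second objection is that no loss has been shown. This stands too. Research Question 1 asks whether clients who use substances do worse without asserting it, and substance use may add little beyond the covariates already in the model.

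A reader might infer more than the documents support:

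- *That the Aim 2 intervals are certainly too wide.* This needs an association that the documents do not report. With d at 0.2 or below there is essentially no loss.
- *That up to about 25 of 140 clients are thrown away.* An R² of 15% gives 140/0.85 − 140 = 25, but that counts the extra clients needed to compensate. The information lost is 140 × 0.15 = 21. An R² that high would need a difference of about 0.84 SD even with half the sample using substances.
- *That every Aim 2 interval would narrow.* In a logistic acceptance model the log-odds-ratio interval would not.

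**Conclusion.** The omission is plain in the text: substance use is the only urn factor that Aim 2 does not adjust for. Its consequence is conditional and small. For attendance and satisfaction the Condition interval is wider by nothing to about 7% across the assumed range, with 1.6% to 2.7% at a moderate association, and by less with therapist clustering. For medication acceptance the effect depends on the scale: a slight gain in power on the odds-ratio scale, or an interval 0.5% to 3.5% wider without substance use on the risk-difference scale.

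The associations, acceptance rates, alpha, power and intraclass correlation used here are all assumptions; the documents supply only N, the equal split and the prevalence range. Missing data were not modelled. The point is one of efficiency and of consistency with Aims 1 and 3, and does not suggest that Aim 2 would give biased or anti-conservative results.

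**What to change.** In the Aim 2 plan, name baseline substance use (yes/no, as defined for the urn) as a covariate in every model, in addition to the nuisance list. State that it is the same variable as the SU+/SU− predictor of Aims 1 and 3, since the documents use different labels. Include it whether or not the baseline comparison finds a difference.

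The cost is one sentence and one degree of freedom. The variable is already needed to run the urn, so no new data are collected. If substance use turns out not to be prognostic, the interval widens by about 0.4% (√(138/137) = 1.004).

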This parametric comparative trial will randomly assign 140 inner-city adolescents with ADHD to (1) CASH-AA Only or (2) CASH-AA + MIP. Treatment will occur in community behavioral health clinics. All participants will receive behavioral interventions (CASH-AA): family psychoeducation in ADHD symptoms, executive functioning, and developmental impacts; family-based motivation and ADHD accommodation interventions; and academic training focused on home environment support and organizational skills. Half of the participants

will also receive medication decision-making interventions (MIP): ADHD medication psychoeducation, family decision-making interventions, and (for those who elect to start medication) coordinated medication management. Half of the sample will have comorbid substance use problems. Treatment will occur in three community clinics; therapists will be randomly assigned to study condition. Caregivers and adolescents will complete assessments at baseline, 3, 6, and 12-month follow-up. Multilevel modeling will compare the effectiveness of each condition on key patient and service use outcomes. Patient-centered analyses will explore differential treatment effects based on (a) Medication decision (yes/no); (b) Substance use comorbidity (yes/no); (c) Race/Ethnicity (Hispanic, African American).

Quantitative outcome analyses will test for service use effects, symptom reduction, and quality of life improvements that are primary reasons for seeking clinical services. Qualitative interviews will document family-specific rationale for decisions about medication, compliance with behavioral and medication interventions, and suggestions for improving services and service integration. Note that families assigned to CASH-AA Only will retain the option of pursuing ADHD medication through treatment-as-usual procedures at their respective clinic. Similarly, families assigned to CASH-AA + MIP will not be required to start ADHD medication. Instead, they will receive informed-choice interventions and can choose when and if to start medication; the study will assess the impact of these decisions on clinical outcomes.

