Based on 20 years of experience engaging high-risk adolescents and their families into longitudinal research, we expect to have rates of missing assessment data on outcome variables between 10-15%. All proposed analyses involving client outcome data will be carried out in Mplus, which provides full information maximum likelihood estimation (MLE), which produces unbiased parameter estimates under the assumption that data are missing at random. Moreover,

MLE outperforms other missing data approaches, such as listwise deletion, even when MAR is not met.

Risks And Benefits

Potential Study Risks

Potential Risks for Client Participants: Research Interviews and Treatment Session Recording

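### In the single-outcome Aim 2 models maximum likelihood is complete-case analysis, so its claimed advantage over listwise deletion does not apply there, and no sensitivity analysis for departures from MAR is planned

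*Combined protocol and SAP*

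**What the plan says.** Under Analytic Plans for Missing Data, the combined protocol and SAP gives the expected loss: "we expect to have rates of missing assessment data on outcome variables between 10-15" percent. Client outcomes are to be analysed by full information maximum likelihood in Mplus, "which produces unbiased parameter estimates under the assumption that data are missing at random". The section then adds, without limiting it to any model, that "MLE outperforms other missing data approaches, such as listwise deletion, even when MAR is not met".

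The section on the Aim 2 outcomes analyses "time-invariant client outcomes: treatment attendance, medication acceptance, and client satisfaction (averaged across caregiver and adolescent"). Each outcome has its own model, with Condition and the baseline nuisance covariates as predictors, and "missing data will be handled with robust maximum likelihood estimation (see below"), which points to the statement above.

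Under Preliminary Analyses and Refuser Analyses there is one check on loss to follow-up: "Logistic regression will examine potential biases due to failure to contact clients at follow-up on baseline characteristics", as well as on study condition and interactions.

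The plan names no auxiliary variables, multiple imputation, pattern-mixture or selection model, or delta adjustment.

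**The concern.** The plan gives one general reason for confidence in ML when MAR fails, and applies it to two kinds of model. ML gains over listwise deletion by using other measurements on the same client. The Aim 1 growth models have such measurements in the other waves. The Aim 2 models have one outcome per client and nothing else measured after baseline, so there is nothing to gain from.

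At stake is an Aim 2 result, mainly for satisfaction, that is reported as protected by ML when it is a complete-case result. For Aim 1, doing better than listwise deletion is not the same as being unbiased, and the plan offers no way to see how far a conclusion depends on MAR.

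**Working it through.** **Inputs.** From the Project Abstract: the study "will randomly assign 140 inner-city adolescents with ADHD to (1) CASH-AA Only or (2) CASH-AA + MIP", and "Half of the participants" also receive the medication component, so about 140/2 = 70 per arm. From the missing-data section: 10-15% missing. The plan gives no alpha, power, SD or effect size, so it has no figure of its own to reproduce. All shifts and missingness mechanisms below are assumptions.

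**Step 1: likelihood in an Aim 2 model.** Let y be the outcome, c Condition, x the baseline covariates (taken as complete) and β the coefficients. A client with y observed contributes f(y | c, x; β). A client with y missing contributes ∫ f(y | c, x; β) dy = 1 (a sum if y is binary), which does not contain β. The maximum is therefore the one obtained from observed clients alone. A therapist random effect does not alter this, because the missing y also integrates out of the joint density for that therapist's clients. The sandwich estimator brings in no information on a missing outcome.

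**Step 2: numerical check.** In 200 simulated trials (70 per arm, three complete covariates, one outcome lost not at random), full-information ML was compared with least squares on observed cases. The largest difference in any coefficient was about 4 × 10⁻¹³, which is rounding error. If the 10-15% applies to an outcome, 140 × 0.10 = 14 to 140 × 0.15 = 21 clients add nothing to its Condition estimate, leaving 126 to 119.

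**Step 3: which Aim 2 outcomes are exposed.** The section on service utilization and satisfaction takes session counts and prescriptions from site contact logs, so a rate for assessment data may not apply to them. They can still be missing, because the section on risks for therapists makes chart data depend on a signed release. Satisfaction comes from questionnaires completed by adolescents and caregivers and is the clearest case. The plan does not say how it is scored when only one of the two responds.

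**Step 4: repeated measures.** In a large simulated sample with four waves, about 12% were missing at the last wave, with loss depending on the unseen value in the Integrated arm only. The true difference was 0.40. A joint normal ML model gave 0.48 and complete cases gave 0.58. ML is better here, as the plan says, but still biased.

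**Step 5: size.** Let m be the share missing in an arm and δ the amount by which its missing values are worse than MAR predicts. For a contrast at one time point, bias in favour of Integrated = m(Int) × δ(Int) − m(Beh) × δ(Beh). With δ(Beh) = 0:

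| δ(Int) | 10% missing | 15% missing |
|---|---|---|
| 0.25 SD | 0.025 SD | 0.0375 SD |
| 0.5 SD | 0.05 SD | 0.075 SD |
| 1.0 SD | 0.10 SD | 0.15 SD |

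With equal m and δ in both arms the terms cancel. With δ = 0.5 in both arms but 15% against 10% missing, the bias is 0.075 − 0.05 = 0.025 SD.

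A large single-outcome simulation agrees. With a true effect of 0.40 SD and loss rising with worse outcome in the Integrated arm only (logit slope 1 per SD), the estimate was 0.49 at 10% missing and 0.53 at 15%. With the same mechanism in both arms it was 0.40 at either rate.

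**Step 6: the attrition regression.** It relates loss to observed variables and can show differential attrition. It cannot show whether loss depends on the unseen outcome, and the plan attaches no change in the outcome analysis to that possibility.

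**The case against.** Four points weigh on the other side.

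- **The sentence can be right for Aim 1.** A reader might infer that the statement is wrong throughout and that the main results rest on it. The documents do not support this. The Aim 1 outcomes are four-wave growth models, where other waves inform a missing one, and Step 4 favours ML there.
- **Follow-up does not depend on treatment.** The paragraph on linking to treatment has research staff interview every randomized family whether or not it attends. This weakens the path from disengagement to missing outcomes. It does not remove the 10-15% that the plan itself expects.
- **MAR cannot be tested from the data.** A reader might fault the plan for not testing it, or for offering the attrition regression as proof of it. The plan makes no such claim for that regression. The gap is the lack of a sensitivity analysis.
- **The illustrated bias is small.** With 126 or 119 clients, SD 1 and no clustering, the standard error of a difference is √(2/63) = 0.178 or √(2/59.5) = 0.183. The bias is then 0.05/0.178 = 0.28 to 0.075/0.183 = 0.41 standard errors. At an assumed two-sided 5% level, the error rate would rise to about 6-7%.

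These points narrow the concern to satisfaction in Aim 2 and to a missing sensitivity analysis in Aim 1. They do not answer Step 1, which follows from the models as written.

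**Conclusion.** The concern holds in this limited form. For the separate single-outcome Aim 2 regressions, ML equals complete-case analysis on the outcome, and the unqualified statement does not apply. This needs only complete covariates and no auxiliary variables. The main exposure is satisfaction. For Aim 1 the statement can stand, but ML may be biased if MAR fails, and nothing in the plan shows by how much.

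The size is illustrative: 0.05 to 0.075 SD if 10-15% are missing and dropouts in one arm only are 0.5 SD worse than MAR predicts, and near zero if the same mechanism acts equally in both arms. The Aim 1 figure refers to a contrast at a single time point; the effect on a slope depends on which waves are missing.

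Two further inferences are tempting but unsupported. One is to express the bias as a share of a detectable difference, which the plan does not state. The other is to read 10-15% as a count of families lost, since the plan gives it as a rate of missing assessment data. This is a worthwhile, inexpensive improvement and not a flaw that undermines the trial.

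**What to change.** 1. Limit the statement about ML and listwise deletion to the repeated-measures models.
2. For Aim 2 satisfaction, and any other Aim 2 outcome with missing values, bring in auxiliary variables already collected: sessions attended, interim interview scores and baseline severity. Use ML with auxiliary variables or multiple imputation. Do not add them as covariates of the Condition effect, because attendance and interim scores arise after randomization and may be affected by Condition. This makes MAR more plausible but does not guarantee it. State also how satisfaction is scored when one reporter is missing.
3. For Aim 1, add a delta-adjusted sensitivity analysis. Shift imputed values by 0 to 0.5 SD in the Integrated arm, then in both arms, and report the shift at which the conclusion changes.

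The cost is a change of wording and a modest amount of extra analysis. No new data are needed.
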